8.2 Definition of Serious Adverse Event (SAE)

A participant-reported AE that results in any of the following outcomes is defined as a Serious Adverse Event:

- Death,
- Life-threatening adverse experience*,
- Inpatient hospitalization or prolongation of existing hospitalization,
- Persistent or significant disability/incapacity,
- Congenital anomaly/birth defect, or cancer, or

- Any other experience that suggests a significant hazard, contraindication, side effect or precaution that may require medical or surgical intervention to prevent one of the outcomes listed above,
- Event that changes the risk/benefit ratio of the study.

*A life-threatening adverse experience is any AE that places the patient or participant, in the view of the investigator, at immediate risk of death from the reaction as it occurred, i.e., it does not include a reaction that, had it occurred in a more severe form, might have caused death.

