At baseline and 12 weeks, a Recent Health Survey with questions from the NCI Patient Reported Outcomes version of the Common Terminology Criteria for Adverse Events (PRO-CTCAE) Measurement System will be used to collect adverse events (AEs) by self-report in study participants.

At 0 and 12-weeks, we will use validated surveys to measure theoretical constructs: the Food Security module from the National Health Interview Survey and a modified Food Beliefs survey (which includes self-efficacy, social support, self-monitoring, etc.).

At 12-weeks, we will assess usability and acceptability of the intervention via the System Usability Scale (SUS), Acceptability of Intervention Measure (AIM), Intervention Appropriateness Measure (IAM), and the Feasibility of Intervention Measure.³¹ The System Usability Scale (SUS) is a valid and reliable 10-item tool for measuring usability.³² The acceptability of each intervention component (e.g., behavior change messages, whole grain intake messages, educational material, food security support) will be evaluated separately.

End of study interview (optional)

Participants may be invited to complete an optional 15 to 30-minute end of study interview to obtain open-ended, qualitative feedback.

8 Adverse Events and Serious Adverse Events

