8.1 Definition of Adverse Event (AE)

An adverse event (AE) is defined as any untoward medical occurrence associated with the use of an intervention in humans, whether or not considered intervention related.

Adverse event assessment:

A Recent Health Survey with modified questions from the NCI Patient Reported Outcomes version of the Common Terminology Criteria for Adverse Events (PRO-CTCAE) Measurement System will be used to collect AEs by self-report in study participants. The survey measures participant-reported frequency, severity, and interference of expected symptoms and also allows the participant to report the severity of unexpected symptoms. Most symptoms are graded on a 5 point Likert scale ranging from 0 to 4. Frequency responses are assessed by the question "How often do you have [symptom]?" and include: Never, Rarely, Occasionally, Frequently, and Almost constantly. Severity responses are assessed by the question "What was the severity of your [symptom] at its worst?" and include: None, Mild, Moderate, Severe, Very Severe. Interference responses are assessed by "How much did [the symptom] interfere with your usual or daily activities?" and include: Not at all, A little bit, Somewhat, Quite a bit, and Very much. For this study, assessments of frequency, severity, and interference are based on a 12-week recall period.

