8.3 Classification of Adverse Events

8.3.1 Severity

Severity of expected, non-serious AEs will be assessed using the PRO-CTCAE severity responses by the question “What was the severity of your [symptom] at its worst?” and include: None, Mild, Moderate, Severe, Very Severe.

Any participant-reported event that is deemed to be an SAE will be graded according to the Common Terminology Criteria for Adverse Events (CTCAE) v5.0, as developed and revised by the Common Therapy Evaluation Program (CTEP) of the National Cancer Institute.

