8.6 Documenting and Reporting of Adverse Events

Adverse Events that are deemed to be SAEs will be documented in the study Case Report Forms (CRFs) and reported to the IRB, HDFCCC DSMC, and collaborators in accordance with all applicable institutional and regulatory requirements.

9 Statistical Considerations

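### The SAE definition in 8.2 covers only participant-reported events, so a serious event learned solely from a relative, clinician or chart falls outside it, although 8.1 sets no such limit

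*Combined protocol and SAP*

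**What the plan says.** Section 8.1 gives the general definition: "An adverse event (AE) is defined as any untoward medical occurrence associated with the use of an intervention in humans", regardless of whether the event is judged related. It names no source. The same section then describes the collection tool, a Recent Health Survey built on PRO-CTCAE items, which "will be used to collect AEs by self-report in study participants".

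Section 8.2 narrows the source: "A participant-reported AE that results in any of the following outcomes is defined as a Serious Adverse Event". Death heads the list of outcomes, which also includes "Inpatient hospitalization or prolongation of existing hospitalization".

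Section 8.3.1 carries the same condition into severity grading: "Any participant-reported event that is deemed to be an SAE will be graded according to" CTCAE v5.0.

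The sections on attribution (8.3.2), DSMC review (8.4) and documentation and reporting (8.6) refer to SAEs without naming a source. Section 8.6 adds that reporting follows the institutional and regulatory rules that apply.

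On timing, section 7.1 places the survey at two points: "At baseline and 12 weeks, a Recent Health Survey". Footnote 3 of the schedule in 6.1, and section 6.2.3, allow medical records to be obtained once there is an SAE.

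**The concern.** An SAE definition should depend on what happened to the participant and not on who told the study team. Here the source of the information is part of the definition, and the sections that follow take the term SAE from it. The condition bears hardest on people who are too ill to respond or who have died, because news of them is most likely to come from someone else.

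The situation is foreseeable. Staff phone or e-mail participants who stop responding (5.3, 5.5), and a relative may answer. Staff may also review medical records at screening (6.2.1). Section 4.1.1 sets no stage limit, 4.1.2 lists no exclusions, and recurrence and metastases are among the items abstracted. A serious illness during the study period is therefore plausible even though the intervention is low risk.

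What is at stake is the completeness of the SAE record and the consistency of what reaches the DSMC and the IRB.

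**Working it through.** No arithmetic applies. The plan states no figure for SAEs, and the point depends on no sample size, power or effect assumption. The check is to follow different routes of information through the sections.

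| How staff learn of the event | AE under 8.1? | SAE under 8.2? | Graded under 8.3.1? | Attribution, DSMC review, reporting (8.3.2, 8.4, 8.6)? |
|---|---|---|---|---|
| Participant reports an event that led to hospitalization, by survey or by contacting staff | Yes | Yes | Yes | Yes |
| Participant reports an event and later dies of it | Yes | Yes | Yes | Yes |
| Relative reports a death; the participant had reported no preceding event | Yes | No | No, by explicit wording | No, but only through the 8.2 definition |
| Clinician or chart reveals a hospitalization the participant never reported | Yes | No | No, by explicit wording | No, but only through the 8.2 definition |

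The second row turns on grammar. In 8.2 the condition attaches to the adverse event, and the outcome is what that event results in. A death that follows a reported event therefore meets the definition.

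The last two rows hold the gap. The events qualify under 8.1 and fail under 8.2 solely because of who supplied the information.

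Next, does any other section close the gap?

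- 6.1 footnote 3 and 6.2.3: records may be collected once an SAE is known. This follows up an SAE; it does not add records as a source for identifying one.
- 5.5: an unreachable participant is classed as lost to follow-up. No check of vital status or hospitalization is described.
- 8.4: the DSMC reviews SAEs where there are any, so the event must first be classed as one.
- 8.6: reporting applies to adverse events deemed SAEs, under external rules. It does not say that an event from another source is to be so deemed.

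None of these widens 8.2. The restriction on grading is stated outright; the restriction on the later steps is inherited.

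**The case against.** The strongest reply is that the adjective merely describes how data arrive in a remotely delivered, survey-based study and was never meant to exclude anything. Section 8.1 defines adverse events broadly, 6.1 footnote 3 speaks of an SAE being observed, 8.6 invokes institutional and regulatory requirements, and 10.1 binds the principal investigator to GCP/ICH. A competent team told of a death would probably report it. That is a fair account of likely practice, and it is why the effect on reporting should be called indirect. It does not change the text. The condition stands in both the definition and the grading sentence, and a protocol should not rely on staff departing from its wording.

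It can also be said that little depends on this. The study is described as minimal risk, intervention-related SAEs are not expected (8.3.2), section 2 has no safety objective, and 9.2 plans no adverse event analysis. All of that stands, and it limits the weight of the point.

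Three stronger readings are tempting, and the documents do not support them:

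- A reader might infer that no death can ever be an SAE. As shown above, a death resulting from an event the participant had reported does qualify.
- A reader might infer that anyone who misses the week-12 survey can have no reportable SAE. Participant report is not confined to that survey: participants may contact the team at any time (1.5), are given a phone number and e-mail address (5.3), and use a two-way messaging platform (5.1).
- A reader might apply the 20% drop-out in 9.1.1 to 60 participants (0.20 × 60 = 12) and treat 12 as the size of the problem. That rate is a planning assumption for the paired t-test on grain intake. It forecasts neither missing health surveys nor serious events, and rewording the definition would not change how many surveys are missed.

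**Conclusion.** The point holds as an inconsistency in the safety definitions. Section 8.2 is narrower than 8.1 on source, and 8.3.1 repeats the narrowing. A serious outcome with no preceding participant-reported adverse event, known only through a family member, clinician or record, fails the SAE definition. It is excluded from grading by express wording, and from attribution, DSMC review and CRF/IRB reporting by inheritance.

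The conclusion rests on reading the definition as written and on finding no other provision that extends it. Its size in events cannot be estimated, because the documents give neither an SAE rate nor the share of serious events likely to be learned from others. The consequence is confined to the SAE record and its oversight. The feasibility and acceptability criteria, the diet comparisons and the power statement do not depend on it. It is a modest point, but worth correcting because the rule, if followed, would omit serious events.

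**What to change.** In 8.2 and 8.3.1, replace the participant-reported condition with wording that covers any adverse event, however the study team learns of it: from the participant, a family member, a clinician or a medical record. Then check that 8.1, 8.2, 8.3.1 and 8.6 agree on the source of events. Sections 8.3.2 and 8.4 need no edit, since they take their scope from 8.2.

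Leave the survey schedule unchanged. The amendment settles which known events count as SAEs; it does not add active follow-up of people who do not respond, and should not be presented as doing so.

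The cost is two wording changes, with the usual amendment and IRB approval under 10.4. No visits, surveys or staff are added. The only foreseeable downside is possibly a few more SAE forms.

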8.3 Classification of Adverse Events

8.3.1 Severity

Severity of expected, non-serious AEs will be assessed using the PRO-CTCAE severity responses by the question “What was the severity of your [symptom] at its worst?” and include: None, Mild, Moderate, Severe, Very Severe.

Any participant-reported event that is deemed to be an SAE will be graded according to the Common Terminology Criteria for Adverse Events (CTCAE) v5.0, as developed and revised by the Common Therapy Evaluation Program (CTEP) of the National Cancer Institute.

8.3.2 Attribution of SAEs

Serious adverse events are further given an assignment of attribution or relationship to study intervention. Attribution categories are:

- **Definite** – The serious adverse event is clearly related to the study intervention.
- **Probable** – The serious adverse event is likely related to the study intervention.
- **Possible** – The serious adverse event may be related to the study intervention.
- **Unrelated** – the serious adverse event is clearly not related to the study intervention.

SAEs attributed to the intervention are not expected for this minimal risk study, but will be monitored, should they occur.

8.3.3 Expectedness

An adverse event is considered unexpected if it is not listed at the specificity or severity that has been observed, or the event is not consistent with the risk information described in the general investigational plan or elsewhere in the current application.

8.4 Adverse Events Monitoring

This study is a minimal risk level study that does not require monitoring by the HDFCCC Data and Safety Monitoring Committee (DSMC) as per the National Cancer Institute-approved Data and Safety Monitoring Plan. Ultimately, the PI is responsible for the safety and conduct of this study. However, the DSMC will provide Serious Adverse Event (SAE) review (if applicable), as well as review of all protocol violations and consent incident reports prior to submission to the IRB.

8.5 Follow Up of Adverse Events

All participants who experience adverse events will be followed with appropriate medical management in accordance with standard of care until resolved or stabilized.

8.6 Documenting and Reporting of Adverse Events

Adverse Events that are deemed to be SAEs will be documented in the study Case Report Forms (CRFs) and reported to the IRB, HDFCCC DSMC, and collaborators in accordance with all applicable institutional and regulatory requirements.

9 Statistical Considerations

9.1 Sample Size Considerations

9.1.1 Sample Size and Power Estimate

Sample size: up to 60.

We will consider our study to the median response proportion to text messages that ask for a reply is $\geq 70\%$, and the median Feasibility of Intervention Measure score is 4 or higher. The intervention will be determined acceptable if median scores on the Acceptability of Intervention and Intervention Appropriateness Measures are ≥ 4 . With our sample size of 60 participants and assuming a standard deviation (SD) for the mean text message response rate of 25% based on prior work,¹⁰ we will be able to detect an average text message response rate of 70% with a 95% CI of 64%-76%.³³

For our secondary outcome of percent of grains that are whole, using a paired t-test to compare mean proportion of total grains that are whole at 0 and 12 weeks, alpha=0.05, a SD=23% for the mean change in proportion of grains that are whole,¹⁰ 20% drop out, and 60 participants, we will have 80% power to detect a $\geq 9\%$ change in proportion of grains that are whole.³⁴

9.1.2 Accrual Estimates

- **Zuckerberg San Francisco General (ZSFG)** is a public safety net hospital that sees 40-50 stage II-III CRC patients/year; 80-90% of whom identify with a racial/ethnic minority group. We estimate 70% will be eligible for the proposed study (~30/year). We aim to enroll 10 participants from ZSFG.
- **UCSF HDFCCC GI Oncology Clinic** sees ~150 cases of stage I-III CRC each year; 40% of whom identify with a racial/ethnic minority group. Based on prior work, ~70% of these patients will be eligible for the proposed study (~105/year). We have also identified over 3,000 people who meet our clinical eligibility criteria using the CTSI Participant Recruitment Program services. We aim to enroll 50 participants from UCSF.

9.2 Statistical Analysis Plans

9.2.1 Primary Analysis (or Analysis of Primary Endpoints)

Descriptive Analyses: We will use descriptive statistics [means (standard deviation, SD) and median (interquartile range, IQR) for continuous variables and proportions for categorical variables] to summarize participant characteristics and baseline variables from the survey data as well as attrition and intervention adherence outcomes. We will quantify text message response rates using medians (interquartile range; IQR) for continuous variables and proportions for categorical variables. We will describe System Usability Scale (SUS) score,

Acceptability of Intervention Measure (AIM), Intervention Appropriateness Measure (IAM), and the Feasibility of Intervention Measure using median (IQR). A score >68 on the SUS is above average usability.

Qualitative data analysis: Audio recordings of interviews will be transcribed, translated to English (if needed), and imported into Dedoose software for structural coding and thematic content analyses.

9.2.2 Secondary Analysis (or Analysis of Secondary Endpoints)

We will compare intake of dietary factors, including whole grains (servings/day), refined grains (servings/d) and total fiber (g/d), before and after the intervention using paired t-tests. For example, for whole grains, our null hypothesis is that there is no difference in whole grain intake, on average, between 0 and 12 weeks. Our alternative hypothesis is that whole grain intake is higher at 12 weeks, on average, compared to 0 weeks. We will use mean (95% CI) and median (IQR) to describe intakes at each time point and change over time for normally and non-normally distributed continuous variables, respectively.

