3.3 Sample Size

We will accrue up to 60 CRC survivors. Participants who withdraw or are otherwise not evaluable will not be replaced.

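### Dietary change is estimated only in participants with both food questionnaires, about 48 of 60, and no all-enrolled sensitivity estimate is planned

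*Combined protocol and SAP*

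**What the plan says.** The secondary objectives (section 2.2) are to estimate the intervention's effect on the percent of grains that are whole and on total fiber. Both are changes from 0 to 12 weeks on the FFQ.

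- **Analysis.** Section 9.2.2 compares dietary factors "before and after the intervention using paired t-tests". The power statement in section 9.1.1 does the same for the powered endpoint, "using a paired t-test to compare mean proportion of total grains that are whole at 0 and 12 weeks".
- **Expected loss.** Section 9.1.1 assumes "20% drop out, and 60 participants". Section 3.3 adds: "Participants who withdraw or are otherwise not evaluable will not be replaced".
- **Missing data.** Section 9.2.1 summarises attrition descriptively. Neither 9.2.1 nor 9.2.2 defines an analysis set, names a method for a missing week-12 FFQ, or plans a sensitivity analysis.
- **Who is meant to be covered.** Section 5 asks everyone, including people who stop answering texts, for the 12-week surveys, partly so that the effect on diet can be estimated. Sections 5.3 and 5.5 provide for up to five automated reminders and three further staff contacts. Section 6.2.4 says there is no follow-up after a participant discontinues the intervention.
- **Other data planned.** All participants have baseline surveys (section 6.2.1) and are texted daily about the previous day's whole-grain intake (section 5). The secondary analysis does not use the replies.

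**The concern.** A paired t-test needs both measurements, so it is a completers-only analysis even though the plan does not call it one. It answers the question for everyone enrolled only if those who return the second FFQ changed, on average, as much as those who do not. In a text-message diet programme it is plausible that people who leave engaged less and changed less.

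The objective is estimation, and section 1.4 says the results will inform the design of an intervention to be tested in a randomized trial. The size of the estimate is therefore what carries forward. As written, the report would give one figure, describing about four-fifths of participants, with nothing to show how far it depends on the missing fifth.

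**Working it through.** **Inputs.** From section 9.1.1: 60 participants, 20% drop-out, 80% power, alpha 0.05, and "a SD=23% for the mean change in proportion of grains that are whole". The documents give neither the dietary change in drop-outs nor the correlation between replies and FFQ change. Both are assumed below, over a range.

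**1. The plan's own figure.**
- Pairs: 60 × (1 − 0.20) = 48.
- Two-sided detectable change: 23 × (1.960 + 0.842) / √48 = 9.3 points (9.5 with the t distribution). This agrees with the stated 9% after rounding.
- With all 60 it would be 8.3 (8.5 with t).

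The stated figure therefore fits 48 complete pairs, which confirms that the calculation rests on completers.

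**2. Overstatement.** With drop-out fraction d, the all-enrolled mean is (1 − d) × completer change + d × drop-out change. The completers-only mean exceeds it by d × (completer change − drop-out change). For completers changing by 9 points and d = 0.2:

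| Assumed change in drop-outs | All-enrolled mean | Overstatement |
|---|---|---|
| 9 | 9.0 | 0 |
| 4.5 | 0.8 × 9 + 0.2 × 4.5 = 8.1 | 0.9 |
| 0 | 0.8 × 9 + 0 = 7.2 | 1.8 |
| −4.5 | 0.8 × 9 − 0.2 × 4.5 = 6.3 | 2.7 |

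Over drop-out of 10% to 30%, the last three rows span 0.45 to 4.05 points.

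**3. Against sampling error (zero-change row).**
- SE = 23/√48 = 3.32, so the bias is 1.8/3.32 = 0.54 SE.
- Coverage of a nominal 95% interval for the all-enrolled mean: Φ(1.96 − 0.54) − Φ(−1.96 − 0.54) ≈ 0.916.

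**4. Effect on the test (zero-change row).**
- Completers: t = 9/3.32 = 2.71 on 47 df, p = 0.0093.
- All 60, with zeros for the 12: mean 7.2; SD = √[(47 × 23² + 48 × 9² × 0.2)/59] = 20.85; t = 7.2/(20.85/√60) = 2.68 on 59 df; p = 0.0096.

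The p-value hardly moves. What changes is the estimated effect, 9.0 against 7.2.

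**5. How far the reply data could help.** In simulation (60 participants, SD 23, true change 7.2, about 20% drop-out driven by engagement, engagement correlated 0.3 with dietary change), the completer mean averaged about 8.35. Regression adjustment on the replies gave:
- replies measuring engagement perfectly and seen for everyone: about 7.2, bias removed;
- replies correlated 0.7 with engagement: 7.80, leaving 0.60 of 1.15 points, about half;
- replies correlated 0.5 with engagement: 8.08, leaving 0.88 of 1.15 points, about three-quarters.

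When engagement is correlated only 0.1 with change, adjustment brings no gain in root mean squared error. If drop-out also depends on the dietary change itself, little of the bias is removed.

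**The case against.** **Direction and size are assumed.** This stands. Nothing in the documents says drop-outs change less. With equal change the bias is zero.

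**The plan already pursues the week-12 FFQ.** This also stands. Not answering texts is not the same as a missing FFQ: sections 5, 5.3 and 5.5 ask non-responders for the surveys and chase them. That may lower the loss or make it less selective. It does not say how the FFQs still missing will be handled, and the plan itself expects 20% drop-out after these efforts.

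**The stakes are modest.** Largely true. This is a secondary endpoint in a single-arm proof-of-concept study. No feasibility or acceptability criterion depends on it, and the zero-change scenario costs about half a standard error. Without a control group, the meaning of a before-after change is uncertain anyway.

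**Reply data cannot repair the estimate.** A reader might infer that the trial will hold what it needs to correct the bias. The documents do not support that. The texts ask about whole grains only, while the powered endpoint also needs refined grains, and fiber is not asked about at all. No pre-intervention text baseline is described. Participants can stop the messages, so replies may be sparse for early leavers. Adjustment also needs missingness to be at random given what is observed.

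**Imputation should not replace the simple comparison.** Fair. With about 48 complete pairs, making a modelled estimate the headline is debatable. It belongs in a sensitivity analysis.

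**Conclusion.** The point holds as a gap in the analysis of a secondary endpoint. The stated method gives a completers-only effect size with a fifth of participants expected to drop out, and no sensitivity analysis shows what that implies for everyone enrolled. For a 9-point completer change at 20% drop-out, the overstatement is 0.9 to 2.7 points if drop-outs change by between 4.5 and −4.5 points, and 0 if they change as completers do.

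Two stronger readings should be avoided. A reader might conclude that the planned estimate is biased upward; the documents show only that it could be. A reader might also conclude that the significance test is unsound; in the zero-change scenario p moves only from 0.0093 to 0.0096, so the effect there is on the size of the estimate. The primary feasibility and acceptability result is not affected.

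**What to change.** In section 9.2.2, keep the paired t-test, label it as the completer analysis, and state the analysis set. Then add:

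1. **An all-enrolled estimate assuming no change** in participants without a week-12 FFQ. It needs no reply data. It is a reference scenario and not a strict lower limit, since drop-outs could worsen.
2. **A sensitivity analysis** by multiple imputation or a likelihood-based model, using baseline FFQ, key baseline characteristics, reply rate and, where available, reported daily whole-grain intake. State the missing-at-random assumption. A mixed model on the two FFQ values alone would add little; any gain comes from the additional variables.
3. **A comparison of baseline and reply data** by week-12 FFQ completion, so that readers can judge how selective the loss was.

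Also clarify, between sections 5 and 6.2.4, whether participants who discontinue the messages are still asked for the week-12 surveys.

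The cost is a few lines of text, a little more analysis and a possibly less favourable figure. No new data collection is needed.
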